7.2 Planned Analyses

We will assess training efficacy using an intent-to-treat analysis including all eligible cases. First, to determine randomization effectiveness, differences in baseline demographic characteristics will be assessed between the immediate training and waitlist control conditions using t -tests for continuous measures and chi-square tests for categorical measures. Any differences in baseline demographic characteristics between the groups will be retained as covariates in subsequent analyses. Dependent variables, all of which are assessed as continuous outcomes documenting domains of Clinical Knowledge and Skills of LGBTQ-affirmative CBT, will be assessed for normality using skewness and kurtosis thresholds of ± 2 . If any continuous outcomes are found to be non-normally distributed, we will transform these variables for further statistical tests and reassess skewness and kurtosis after transformation.

In a first set of analyses, we will use linear mixed models with maximum likelihood estimation and we expect to utilize a compound symmetry covariance structure (although final covariance structure will selected based on fit criteria, i.e., lowest Akaike information criterion [AIC]) to test the Condition \times Time interaction for all training outcomes). To do so, we will limit the data to baseline (time = 0) and 3 months post-baseline assessment (time = 1) and examined the Condition \times Time interaction effect of receiving immediate training (condition = 1) versus receiving the 3-month waitlist (condition = 0). Thus, the estimate of interest compared pre-training to immediate post-training outcomes in the immediate training group to pre-waitlist and immediate post-waitlist outcomes in the waitlist control group. Effect sizes (d) for linear mixed models will be calculated as mean pre–post change in the immediate training group minus the mean pre-post change in the waitlist control group, divided by the pooled baseline standard deviation.

In a second set of analyses, we will conduct a pooled analysis whereby data from all participants will be pooled to examine change in outcomes from immediate pre-training to post-training using paired t -tests (i.e., baseline to 3 months post-baseline for the immediate training group and 3-months post-baseline to 6-months post-baseline for the waitlist-control group). Pooled analyses are useful in waitlist-controlled studies (where all participants ultimately receive the intervention) to assess the pre-post effect of the intervention in a larger sample than the condition \times time analyses allow. Effect sizes (d) for pooled analyses will be calculated as $2t/\sqrt{df}$.

Finally, we will assess the longer-term persistence of observed intervention effects by limiting analyses to 3-months post-baseline (time = 1) and 6-months post-baseline (time = 2) among participants in the immediate training condition (condition = 1), the only participants to have completed assessments 3-months after receiving the training. Specifically, we will examine the significance of changes between time points for all outcomes across self-report and deliberate practice of Clinical Knowledge and Skills of LGBTQ-affirmative CBT. Results will be evaluated at $p < .05$. We will report means, standard errors, and 95% confidence intervals.

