NCT04559698

Title of Research Project: Assessing mental health providers' clinical knowledge and skills via an online training on LGBTQ-affirmative cognitive-behavioral therapy

Date: 12.7.21

Assessing Mental Health Providers Clinical Knowledge and Skills Via an Online Training on LGBTQ-affirmative Cognitive-behavioral Therapy

Statistical Analysis Plan

Feasibility and Acceptability

Feasibility was assessed in terms of training attendance. Acceptability was assessed in terms of a 7-item measure we created for the present study presented to participants immediately following the intervention (immediate $n = 52$, waitlist control $n = 44$). Sum scores were taken for each participant, and means and standard deviations were recorded for each condition to determine training acceptability.

Intervention Efficacy

Intervention efficacy was assessed using an intent-to-treat analysis and included all participants ($n = 121$). First, to test the effectiveness of randomization, we examined differences in baseline participant demographic and professional characteristics between the immediate intervention condition ($n = 61$) and waitlist control ($n = 60$) using t -tests for continuous measures and chi-square tests for categorical measures. Age, fulltime employment status, and number of years working in LGBTQ mental healthcare differed between conditions ($p < .10$), with the waitlist control group containing participants with a younger mean age, who were less likely to be working fulltime, and who reported fewer years working in LGBTQ mental healthcare. Thus, we included fulltime employment status and number of years working in LGBTQ mental health care as covariates in subsequent analyses. We did not include age as a covariate because of its high correlation ($r = .50$) with number of years working in LGBTQ mental healthcare. Dependent variables were assessed for normality using skewness thresholds of ± 2 and kurtosis

thresholds of ± 7 (Byrne, 2010; Hair et al., 2010), and all dependent variables were considered normal except simulated practice skills for general CBT. To meet model assumptions of normal distribution, scores on the simulated practice skills for general CBT scale were square-root transformed prior to efficacy analyses.

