To examine intervention efficacy, we used linear mixed models with maximum likelihood estimation and an unstructured covariance matrix to test the Condition \times Time interaction for all intervention outcomes including LGBTQ cultural competence, LGBTQ cultural humility, minority stress knowledge, LGBTQ-affirmative CBT knowledge, LGBTQ-affirmative CBT skills familiarity, LGBTQ-affirmative CBT skills use, LGBTQ-affirmative simulated practice skills, and general CBT simulated practice skills. Primary analyses between conditions were limited to baseline (time = 0) and 4-months post-baseline assessment (time = 1; changed from 3-months post-baseline prior to the beginning of the study) and examined the Condition \times Time effect of receiving immediate intervention (condition = 1) versus receiving the 4-month waitlist (condition = 0). Thus, these models compared pre-intervention and immediate post-intervention outcomes in the immediate intervention group with 4-months pre-intervention and pre-intervention outcomes in the waitlist control group. Effect sizes (d) for linear mixed models were calculated as mean pre-post change in the immediate intervention group minus the pre-post change in the waitlist control group, divided by the pooled baseline standard deviation (Morris, 2008).

To examine longer-term persistence of intervention efficacy, we secondarily limited analyses to the immediate intervention group and compared 8-months post-baseline assessment (time = 2; changed from 6-months post-baseline prior to the beginning of the study) to both baseline (time = 0) and 4-months post-baseline assessment (time = 1). Differences between

baseline and 4-month follow-up would indicate delayed efficacy if differences were detected at 4-month follow-up but not post-intervention. Differences between 4-months post-baseline assessment and 8-months post-baseline assessment would reveal whether efficacy was maintained, increased, or decreased from 4-months post-baseline assessment. Effect sizes (d) were calculated as mean change from baseline- and 4-months post-baseline to 6-months post-baseline divided by the baseline immediate intervention standard deviation accounting for correlation between time points (Morris & DeShon, 2002).

All results were evaluated at $p < .05$. We report means, standard errors, 95% confidence intervals, and effect sizes.

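### Protocol 7.2 converts a paired t to d with 2t/√df, an independent-groups formula, so the planned pooled d would be inflated and off the scale of the Condition × Time d

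*Protocol*

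**What the plan says.** Protocol section 7.2 (Planned Analyses) sets out a first and a second set of efficacy analyses, each with its own d.

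- **Randomised comparison.** The Condition × Time d takes the "mean pre–post change in the immediate training group minus the mean pre-post change in the waitlist control group", "divided by the pooled baseline standard deviation".
- **Pooled analysis.** Here "data from all participants will be pooled to examine change in outcomes from immediate pre-training to post-training using paired" t-tests. Each participant contributes one pair: baseline and 3 months in the immediate arm, and "3-months post-baseline to 6-months post-baseline for the waitlist-control group". The effect size rule follows: "Effect sizes (d) for pooled analyses will be calculated as $2t/\sqrt{df", i.e. 2t/√df.

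The protocol does not say that the second d is on a different scale from the first.

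The SAP (Intervention Efficacy) keeps the pooled-baseline-SD d for Condition × Time. For its within-arm persistence analysis it uses mean change "divided by the baseline immediate intervention standard deviation accounting for correlation between time points". It contains neither the pooled paired analysis nor 2t/√df, and it does not say that either was dropped.

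**The concern.** The factor 2 in 2t/√df comes from the standard error of a difference between two independent means. A paired t has no such factor, because its standard error is already that of a mean change. Applying the conversion to a paired t therefore doubles a quantity that was already standardised, and that quantity is standardised by the SD of change, not by a raw-score SD.

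If the analysis is run as written, the uncontrolled pre-post d would look larger than the same raw change expressed on the scale of the randomised comparison. The excess grows with the pre-post correlation, so it would also differ between outcomes for reasons unrelated to the training effect. Someone reading the two sets of d values side by side could take the pooled effect to be the stronger one on arithmetic alone.

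**Working it through.** The documents state no numerical pooled d, so there is no figure to reproduce. The check is algebraic.

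**Inputs from the documents**
- Paired t-tests and d = 2t/√df; pooled baseline SD for the Condition × Time d (protocol 7.2).
- Planning effect 0.66 and N = 76 (protocol 7.1); 121 participants in the efficacy analysis (SAP, Intervention Efficacy).
- n = 96 = 52 + 44, from the acceptability respondents, "immediate $n = 52$, waitlist control $n = 44" (SAP, Feasibility and Acceptability). This is illustrative only; it is not a documented count of pairs.

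**Assumptions (not in the documents)**
- Pre-post correlation r from 0 to 0.8.
- Equal pre and post SDs, relaxed in step 4.

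**Step 1. Where the formula works.** For two equal independent groups totalling N, t = d·√N/2. With d = 0.66 and N = 80, t = 2.952 and 2t/√(N−2) = 5.903/8.832 = 0.668. The formula recovers d, apart from a small df term.

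**Step 2. With a paired t.** Let d_z = mean change / SD of change. Then t = d_z·√n and df = n − 1, so

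2t/√df = 2·d_z·√(n/(n−1)).

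The multiplier on t/√n is 2.013 at n = 76, 2.011 at n = 96 and 2.008 at n = 121. No assumption about r is needed.

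**Step 3. Against the baseline-SD scale.** Let D = mean change / baseline SD. With equal SDs the SD of change is SD·√(2(1−r)), so d_z = D/√(2(1−r)) and

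(2t/√df)/D = √(2/(1−r))·√(n/(n−1)).

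At n = 96 the last term is √(96/95) = 1.005. Taking D = 0.66 as an example:

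| r (assumed) | t | 2t/√df | ratio to D |
|---|---|---|---|
| 0 | 4.57 | 0.94 | 1.42 |
| 0.3 | 5.47 | 1.12 | 1.70 |
| 0.5 | 6.47 | 1.33 | 2.01 |
| 0.7 | 8.35 | 1.71 | 2.60 |
| 0.8 | 10.22 | 2.10 | 3.18 |

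Converting the same t with t·√(2(1−r)/n) returns 0.66 in every row.

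**Step 4. Unequal SDs.** If post SD = k × pre SD, the ratio is 2/√(1 + k² − 2rk)·√(n/(n−1)). Over r = 0 to 0.8 at n = 96, it runs from 1.57 to 3.35 for k = 0.8 and from 1.29 to 2.79 for k = 1.2. Leaving out the small n term, the ratio falls to 1 only when k = r + √(r² + 3), which is 1.73 at r = 0 and 2.30 at r = 0.5. The post-training SD would have to be that many times the pre-training SD before the inflation vanished.

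**Step 5. Simulation.** With D = 0.66, r = 0.5 and n = 96 (20,000 runs), the formula averaged 1.34, against 0.67 for mean change divided by the pre-training SD.

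**The case against.** The strongest reply is about consequence. The SAP is the later document and is written in the past tense. Its efficacy analyses are mixed models only, and both effect sizes that it defines use a baseline SD. On that reading the formula feeds no listed result, and the defect is confined to a descriptive effect size for a secondary, uncontrolled analysis. This stands, and it limits the weight of the point. It does not correct the protocol text. The SAP records other departures, such as the move from 3 to 4 months, but is silent on this one, so a reader of both documents cannot tell whether a pooled d was computed as the protocol states.

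A second reply is that the two d values would differ anyway: one subtracts the waitlist change and the other does not, and the pooled analysis takes the 3-month visit as the waitlist arm's starting point. That is true, and correcting the standardiser leaves two different estimands. It is a separate difference, though, and does not justify the doubling.

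Third, the larger multipliers rest on assumed r and SDs, and 0.66 is borrowed from the planning of a between-group comparison. This is also fair. Only the factor of about 2 against t/√n is free of assumptions. The direction, however, holds for every r above −1 when the SDs are equal, and step 4 shows how extreme the SD ratio must be to reverse it.

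Finally, section 7.2 promises means, standard errors and 95% confidence intervals, from which a reader could judge the raw change. That softens the effect of a wrong d but does not make the d right.

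**Conclusion.** The concern holds. Section 7.2 names a conversion that does not fit the test it is applied to. Followed as written, it gives about twice t/√n at any r. Relative to mean change over baseline SD, it gives 1.42 to 3.18 times the value for assumed r of 0 to 0.8 with equal SDs, or 1.29 to 3.35 times if the post SD may be 0.8 to 1.2 times the pre SD. These ranges use n = 96, but n hardly matters. The pooled d would share a scale with neither the Condition × Time d nor the SAP's persistence d.

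The error is confined to the pooled effect size. The t statistics, p-values, sample size and randomised comparison do not depend on it, and no reported value is shown to be affected. It should be corrected, but it does not threaten the trial's main conclusion.

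**What to change.** Define the pooled d as mean pre-to-post-training change divided by a stated raw-score SD, with a 95% CI that accounts for the pre-post correlation. Name the SD:

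- the pooled baseline SD of both arms, which matches the Condition × Time d; or
- the immediate pre-training SD (baseline for the immediate arm, the 3-month visit for the waitlist arm), which matches how section 7.2 defines the pairs.

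Say alongside it that the pooled d has no control subtraction, so that a shared standardiser is not read as a shared estimand. If the pooled analysis was dropped, state that in the SAP and remove the formula.

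The cost is one line of text and no new data. The paired data already supply the correlation that the interval needs. The pooled effect size will be smaller than the present formula would give.

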7.2.1 Secondary Objective Analyses (if applicable)

Feasibility of the training will be assessed in terms of training attendance. Acceptability will be assessed in terms of responses to the Acceptability of LGBTQ-affirmative CBT Training Questionnaire that all participants will complete at their immediate post-training time point (3-month post-baseline for the immediate training group and 6-month post-baseline for the waitlist control group). Acceptability analyses will include descriptive statistics including means and medians for quantitative responses. For the qualitative free-response data that will be collected on the acceptability questionnaire, thematic analysis will be used to identify patterns of responses and emergent codes will be categorized into larger themes (Braun & Clarke, 2006).

7.2.2 Analysis of Subject Characteristics (if applicable)

In the baseline assessment, we will collect demographic data including age, race/ethnicity, sex, gender identity, sexual orientation, education level, degree/provider title, and number of years working in mental health generally, as well as number of years working specifically in LGBTQ-focused mental health. Subject characteristics will be reported descriptively utilizing means and standard deviations for continuous variables and proportions for categorical variables.

7.2.3 Interim Analysis (if applicable)

N/A

7.3 Data Relevance

In this study our primary objective is to measure whether a training in LGBTQ-affirmative practice increases MHPs clinical knowledge and skills of LGBTQ-affirmative CBT. The data that we will collect in this study is highly relevant to our primary objective. We will measure self-reported clinical knowledge and skills across several domains including sexual orientation counselor competency, cultural humility, LGBTQ-affirmative CBT skills, minority stress understanding, and LGBTQ-affirmative CBT content understanding. In addition to this self-report data, we will also obtain deliberate practice of LGBTQ-affirmative CBT skills that will include open-ended response to clinical vignettes that will then be coded on a continuous scale. Finally, in alignment with our secondary objective to assess training feasibility and acceptability, we will assess the acceptability of the training through quantitative and qualitative survey items. All data collected as part of this study is highly relevant to our research questions.

7.4 Data Coding

Data will be scored based on each measure's pre-specified ratings scale (see Measures packet). Outcomes utilized in statistical analyses will be continuous sum or mean scores, as applicable.

7.5 Data Analysis Tools

Data will be managed and analyzed utilizing SPSS and SAS version 9.4.

7.6 Data Monitoring

N/A

7.7 Handling of Missing Data

We will assess the LGBTQ-affirmative CBT training efficacy using an intent-to-treat analysis including all eligible cases; therefore, cases with missing data on outcomes will be dropped.

8 Data/Specimen Handling and Record Keeping

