6.1 Study Procedures

A 3-time point longitudinal design will be used for both the immediate training group and waitlist control group with assessment measures administered at each time point (T1: baseline; T2: 3-months post-baseline; T3: 6-months post-baseline). As previously discussed, interested participants will complete an initial online screener. Data collected on this brief online screener will be used to determine eligibility based on the previously listed inclusion criteria, as well as to collect email addresses to contact participants about the training. Data from the initial online screener will not be merged or included with subsequent data collected during the study.

Participants will be contacted via email approximately two weeks prior to the start of the training and informed via the online consent about the research study, including risks and benefits of the study. Participants will still have the option to participate in the training and receive continuing education credits whether or not they consent to and complete the research study measures. The 11 training sessions in terms of content will be no different for those who consent to participate in the study compared to those who choose not to participate in the study. For those who do not provide consent to the study, no data will be collected from these individuals at the three time-point surveys. For those who do provide consent, participants will complete the baseline surveys (T1) via a web-based survey link to the secure Yale Qualtrics survey software. Participants will be told that they do not have to answer any question they do not wish to. Participants will be assigned a unique code number. The use of the unique code will permit linkage of the data being collected across three time points in the study. A master link file will connect participant email addresses to their study code number. The link file will be password protected and only accessible to the PI. All materials will be stored on a password-protected digital folder. Data will be organized in Microsoft Excel, SPSS files, or SAS files and stored on a password-protected computer.

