6.5 Withdrawal Procedures

Of the participants who are eligible and consent to the research study, participants will be able to withdraw from the study at any point. The online consent form will clearly state the voluntary nature of the study and possibility of withdrawal at any point. Additionally, participants will have the option of having their data destroyed.

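### Protocol 7.7 draws from intent-to-treat a rule that drops cases with missing outcomes; this contradicts the all-cases mixed model in Protocol 7.2 and the SAP, and the SAP never withdraws it

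*Protocol*

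**What the plan says.** Protocol 7.7 is one sentence long. It plans "an intent-to-treat analysis including all eligible cases; therefore, cases with missing data on outcomes will be dropped".

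Protocol 7.2 describes the same efficacy analysis without any completeness requirement: "We will assess training efficacy using an intent-to-treat analysis including all eligible cases". The model is given as "linear mixed models with maximum likelihood estimation and we expect to utilize a compound symmetry covariance structure", with the final covariance structure chosen by AIC, fitted to baseline and the first follow-up.

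The SAP is dated about 14 months after the protocol and is written in the past tense. Under Intervention Efficacy it says "Intervention efficacy was assessed using an intent-to-treat analysis and included all participants", with n = 121 (61 immediate, 60 waitlist). The model is a maximum-likelihood linear mixed model with an unstructured covariance matrix. The SAP says openly that the assessments moved from 3 and 6 months to 4 and 8 months. It has no missing-data section, does not mention Protocol 7.7 and names no missingness assumption.

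Two protocol provisions make gaps in the data likely. In 6.1, "Participants will be told that they do not have to answer any question they do not wish to". In 6.5, on withdrawal, "participants will have the option of having their data destroyed".

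**The concern.** An intent-to-treat set that includes every eligible case gives no reason to remove some of them, so the 'therefore' in 7.7 joins two statements that pull in opposite directions. Within that sentence, and again in 7.2, 'cases' are the participants who make up the analysis set. Read the same way in its second half, the sentence prescribes a completers analysis under an intent-to-treat label.

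The choice matters for the Condition × Time estimate. A participant with a baseline but no follow-up contributes nothing to a completers change contrast. In a maximum-likelihood model on all available data, the same participant helps to fix the baseline mean of the arm, from which the follow-up mean is estimated. If dropout depends on baseline score, and its rate or pattern differs by arm, the two analyses estimate different quantities. The completers contrast is then biased. The unstructured maximum-likelihood model is not, provided missingness depends only on what was observed and the model is correct.

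**Working it through.** **Step 1. Who is analysed under each text.** Take a randomised participant with a baseline score and no 4-month score.

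| Source | Rule | This participant |
|---|---|---|
| Protocol 7.7, plain reading | cases with missing outcomes removed | out |
| Protocol 7.2 | all eligible cases, maximum-likelihood mixed model | in |
| SAP, Intervention Efficacy | all 61 + 60 = 121, maximum likelihood, unstructured covariance | in |

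The first row cannot stand with the other two.

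**Step 2. How much is missing.** The documents allow this for the simulated-practice outcomes only.

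Inputs: 121 participants (SAP, Intervention Efficacy); 2 video clips per participant per time point (Protocol 4.2.1); coded responses of 235 at baseline, 189 at 4 months and 163 at 8 months (SAP, paragraph on coding of the practice videos). The SAP's total reproduces: 235 + 189 + 163 = 587. Since 235 exceeds 121, responses are counted per clip.

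Possible responses per time point: 2 × 121 = 242.

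- Baseline: 242 − 235 = 7 missing, 7/242 = 2.9%.
- 4 months: 242 − 189 = 53 missing, 53/242 = 21.9%.
- 8 months: 242 − 163 = 79 missing, 79/242 = 32.6%.

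In participants: at 4 months at most 94 can have both clips coded (189/2, rounded down), so at least 121 − 94 = 27 (22%) lack one or both. At 8 months at most 81 can have both, so at least 121 − 81 = 40 (33%) lack one or both. The number with no response at all is not identified. At least 95 participants (189/2, rounded up) gave a response at 4 months and at least 82 at 8 months, so those with none number 0 to 26 and 0 to 39.

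These counts pool the arms. They do not give missingness by arm at 4 months, missingness in the immediate arm alone at 8 months (the group used for persistence), or missingness on the other six SAP outcomes.

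**Step 3. Whether the choice can move the estimate.** This is an illustration. The model and all its inputs are assumed, some set from document figures.

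Baseline Y0 is standard normal. Follow-up is Y1 = 0.5·Y0 + 0.66·arm + error, where 0.66 is the effect size from Protocol 7.1 and 0.5 an assumed correlation. The probability of being retained is logistic in Y0, with slope 0.5 or 1 per SD in either direction. Retention in the immediate arm is set at 52/61 = 85.2%, on the assumption that the 52 acceptability respondents also answered the clips. For the waitlist arm, baseline clip completion of 235/242 = 0.971 gives (189/(2 × 0.971) − 52)/60 = 75.5%.

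With m1 and m0 the mean baseline of those retained in the immediate and waitlist arms:

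completers contrast = 0.66 + (0.5 − 1)·(m1 − m0)

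If low scorers are retained more often (slope 1), m1 = −0.131 and m0 = −0.209.

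- Same slope in both arms: 0.66 − 0.5 × (−0.131 + 0.209) = 0.621. Over all four slopes: 0.621 to 0.699.
- Dropout related to baseline in the waitlist arm only (m1 = 0): 0.66 − 0.5 × 0.209 = 0.555. Over all four slopes: 0.555 to 0.765.
- Same slope and equal retention: m1 = m0, so 0.660, no bias.

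Maximum likelihood with unstructured covariance, using all baselines, returns 0.660 in each setting.

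**The case against.** The strongest reply is that the SAP has already settled the matter. It is later, it describes what was done, and it reports all 121 participants in a maximum-likelihood model. That cannot be squared with dropping participants, so 7.7 is displaced in substance. This stands for the primary contrast. A reader might infer from 7.7 that the trial ran a completers analysis, or that its result is biased; nothing in the documents shows either. What is left is that the SAP records its changed assessment times but not this change, and leaves unstated the assumption its model relies on.

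A second reply is that, in long-format data, a 'case' may be a single row. Leaving out rows without an outcome is ordinary in a mixed model and agrees with 7.2. This is possible. It sits poorly with the use of the word in the first half of the sentence, and if it is what was meant, the text should say so.

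Some wider criticisms are tempting but do not hold up:

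- The pooled paired t-tests in 7.2 might look uncovered. In fact 7.7 is general, a paired test uses complete pairs by construction, and the SAP does not carry these tests forward.
- The 8-month persistence analysis might look like a separate gap. It follows the model paragraph directly and most naturally uses the same model on the immediate arm, so a clarifying clause is enough.
- The two covariates might be thought to lose participants. Neither document reports a missing covariate value, and permission to skip questions does not show that these were skipped.
- The acceptability counts, 52 of 61 and 44 of 60, might be read as differential dropout. The forms were collected after training, hence at different time points in the two arms, so they do not establish that at 4 months.

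**Conclusion.** The concern holds in a limited form. The rule in Protocol 7.7 is wrong as written, and on its plain reading it conflicts with Protocol 7.2 and the SAP. It is more than an omitted detail, because it prescribes a different analysis from the one planned and reported. The SAP points to the sounder analysis for the primary contrast but leaves the contradictory rule in place.

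Missingness is large enough for the rule to matter: 21.9% of possible simulated-practice responses at 4 months and 32.6% at 8 months. These are shares of responses. Reading them as the share of participants who dropped out goes further than the counts allow.

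The illustration shows only that the two rules can give different estimates. The wider range needs dropout related to baseline in one arm alone, for which the documents give no evidence, and there is no bias with a shared slope and equal retention. The actual size and direction of any bias are unknown, and the conclusion does not depend on the illustrated ranges.

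**What to change.** Replace the sentence in Protocol 7.7, and state in the SAP that its own rule supersedes 7.7. Suggested wording:

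*All randomised participants who have not withdrawn their data are analysed as randomised in the maximum-likelihood mixed model with unstructured covariance, using every available outcome observation under missing at random; participants with baseline only are retained.*

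Add a clause that the same rule applies to the 8-month persistence analysis in the immediate arm. If 7.7 was meant to cover single missing records only, this wording says so.

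The cost is a few sentences, with no new data. If the SAP model was fitted as described, the primary estimate does not change.

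Two additions would help a reader judge whether missing at random is plausible, but they are optional: a table of missingness by arm, outcome and time point, and a sensitivity analysis of the 4-month contrast to departures from missing at random, in a form the sponsor chooses.
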